8.9 Diet

Patients should maintain a normal diet unless modifications are required to manage an AE such as diarrhoea, nausea or vomiting.

8.10 Contraception

Pembrolizumab may have adverse effects on a foetus *in utero*. Furthermore, it is not known if pembrolizumab has transient adverse effects on the composition of sperm. Non-pregnant, non-breast-feeding women may be enrolled if they are willing to use 2 methods of birth control or are considered highly unlikely to conceive. Highly unlikely to conceive is defined as 1) surgically sterilized, or 2) postmenopausal (a woman who is ≥ 45 years of age and has not had menses for greater than 1 year will be considered postmenopausal), or 3) not heterosexually active for the duration of the study. The two birth control methods can be used; two barrier methods or a barrier method plus a hormonal method to prevent pregnancy. Patients should start using birth control from study Visit 1 throughout the study period up to 120 days after the last dose of study pembrolizumab.

The following are considered adequate barrier methods of contraception: diaphragm, condom (by the partner), copper intrauterine device, sponge, or spermicide. Appropriate hormonal contraceptives will include any registered and marketed contraceptive agent that contains an oestrogen and/or a progestational agent (including oral, subcutaneous, intrauterine, or intramuscular agents).

Patients should be informed that taking the study medication may involve unknown risks to the foetus (unborn baby) if pregnancy were to occur during the study. In order to participate in the study they must adhere to the contraception requirement (described above) for the duration of the study and during the follow-up period. If there is any question that a patient will not reliably comply with the requirements for contraception, that patient should not be entered into the study.

8.11 Use in Pregnancy

If a patient inadvertently becomes pregnant while on treatment with pembrolizumab, the patient will immediately be removed from the study. The site will contact the patient at least monthly and document the patient's status until the pregnancy has been completed or terminated. The outcome of the pregnancy will be reported to the Sponsor and to Merck without delay and within 24 hours to the Sponsor and within 2 working days to Merck if the outcome is a serious adverse experience (e.g., death, abortion, congenital anomaly, or other disabling or life-threatening complication to the mother or newborn).

The study investigator will make every effort to obtain permission to follow the outcome of the pregnancy and report the condition of the foetus or newborn to Merck and the Sponsor. If a male patient impregnates his female partner the study personnel at the site must be informed immediately and the pregnancy reported to the Sponsor and to Merck and followed as described above and in Section 8.11.

8.12 Use in Nursing Women

It is unknown whether pembrolizumab is excreted in human milk. Since many drugs are excreted in human milk, and because of the potential for serious adverse reactions in the nursing infant, patients who are breast-feeding are not eligible for enrolment.

8.13 Non-Permitted Medications

Patients are prohibited from receiving the following therapies during the screening and treatment phase of this trial:

- Antineoplastic systemic chemotherapy or biological therapy
- Immunotherapy not specified in this protocol
- Chemotherapy not specified in this protocol
- Investigational agents other than pembrolizumab
- Radiation therapy

Note: Radiation therapy to a symptomatic lesion(s) or to the brain may be allowed at the investigator's discretion.

- Live vaccines within 30 days prior to randomisation and while participating in the trial. Examples of live vaccines include, but are not limited to, the following: measles, mumps, rubella, varicella/zoster, yellow fever, rabies, BCG, and typhoid vaccine.
- Systemic glucocorticoids for a chronic inflammatory disorder. The use of physiologic doses of corticosteroids on a regular repetitive basis for a medical condition may be approved after consultation with the Principal Investigator.

Patients who, in the assessment by the investigator, require the use of any of the aforementioned treatments for clinical management should be removed from the trial. Patients may receive other medications that the investigator deems to be medically necessary.

The exclusion criteria describe other medications that are prohibited in this trial.

There are no prohibited therapies during the follow-up phase.

9. Trial Radiotherapy Treatment

The treatment regimen involves the delivery of a single fraction of highly conformal SABR to 1 to 3 metastases; delivered with either photons, electrons or mixed modalities. The maximal number of metastases within this range should be irradiated, however, at least one metastases defined as measurable disease must not be irradiated. The first dose of pembrolizumab will be delivered either 7 days (+/- 2 days after (ARM 1) or 7 days (+/- 2 days) before (ARM 2) the SABR treatment and will be continued for up to 24 months (34 cycles).

9.1 Megavoltage Radiotherapy

The investigational treatment will be prescribed to the covering isodose, ensuring that 99% of the PTV is covered by 100% of the dose (D99=100%). When this coverage cannot be achieved whilst respecting surrounding organs at risk, a lower coverage of D95=100% is acceptable. Intensity Modulated Radiation Therapy (IMRT) is not compulsory but will be considered if very steep dose gradients have to be achieved or targets 'wrap around' a critical structure. This is the near minimum dose to the target as considered by the International Commission of Radiation Units and Measurements (ICRU) in their report 83(51). Multi-field photon treatment, intensity modulated radiation therapy (IMRT), dynamic conformal arcs, electrons and volumetric modulated arc therapies (VMAT) can all be considered.

A single fraction of SABR approach will be utilized, which is the most commonly used fractionation schedule utilized at the Peter MacCallum Cancer Centre. The dose will be prescribed using a 'stereotactic' paradigm to an isodose line no less than 70% of the maximum dose, aiming for a prescription isodose of 80%. This should result in a maximum dose to the PTV of between 125% and 143%. This allows for larger target dose in homogeneities but results in a steeper dose fall off outside of the target volume.

If more than one lesion is to be treated in a single patient, treatment of all lesions ideally would be given in one setting for patient convenience. However for practical or logistic reasons this may not always be possible and in such cases all lesions should be treated within a time window spanning not more than 7 calendar days. In the case where targets are treated on different days, then treatments should ideally be delivered on consecutive days. Dose for each lesion will be independently verified before treatment and image guidance will be used to ensure accurate patient positioning.

For further details, refer to the SABRseq Radiotherapy Manual.

9.2 Statement of Treatment Aim and Rationale

Treatment rationale is to provide long-term local and distant disease control in patients with NSCLC using a single fraction of stereotactic ablative radiotherapy (to 1-3 sites) in conjunction with pembrolizumab.

9.3 Treatment Schedule

Study therapy should commence within 28 days of patient randomisation on the study. A single dose of 20 Gy should be prescribed, although a single 18Gy fraction can be used as an alternative for a centrally located lung lesion or a spinal lesion with a SINS score of ≥ 7 after review at SABR chart round. Ideally all treatments should be performed on the same day. One or more lesions must be deemed suitable for treatment with SABR; up to 3 lesions may be treated. The choice of treatment sites for SABR is at clinician discretion, but should encompass different types of metastatic sites where possible (e.g. bone and/or lymph node and/or visceral organ). The maximal number of metastases within this range should be irradiated, however, at least one metastases defined as measurable disease must not be irradiated. The use of single 4mg dose of prophylactic dexamethasone prior to SABR treatment is permitted.

10. Trial Pembrolizumab Treatment

Pembrolizumab treatment should begin either 7 days (+/- 2 days) before the first SABR treatment or 7 days (+/- 2 days) after the last SABR treatment

Pembrolizumab 200 mg will be administered as a 30 minute IV infusion every 3 weeks for 34 cycles. Sites should make every effort to target infusion timing to be as close to 30 minutes as possible. However, given the variability of infusion pumps from site to site, a window of -5 minutes and +10 minutes is permitted (i.e., infusion time is 30 minutes: -5 min/+10 min).

Pembrolizumab treatment should be administered on Day 1 of each cycle after all procedures/assessments have been completed as detailed in Sections 8.2 and 8.3. Trial treatment may be administered up to 3 days before or after the scheduled Day 1 of each cycle due to administrative reasons.

All trial treatments will be administered on an outpatient basis.

10.1 Pembrolizumab Dose Modifications and Delays

Adverse events associated with pembrolizumab exposure may represent an immunologic etiology. These adverse events may occur shortly after the first dose or several months after the last dose of treatment. Pembrolizumab must be withheld for drug-related toxicities and severe or life-threatening AEs as per Table 7 below. See Section 8.8 for supportive care guidelines, including use of corticosteroids. Dose reductions are not permitted.

Table 7: Dose Modification Guidelines for Drug-Related Adverse Events

General instructions: 
 1. Corticosteroid taper should be initiated upon AE improving to Grade 1 or less and continue to taper over at least 4 weeks. 2. For situations where pembrolizumab has been withheld, pembrolizumab can be resumed after AE has been reduced to Grade 1 or 0 and corticosteroid has been tapered. Pembrolizumab should be permanently discontinued if AE does not resolve within 12 weeks of last dose or corticosteroids cannot be reduced to ≤ 10 mg prednisone or equivalent per day within 12 weeks. 3. For severe and life-threatening irAEs, IV corticosteroid should be initiated first followed by oral steroid. Other immunosuppressive treatment should be initiated if irAEs cannot be controlled by corticosteroids. 				
Immune-related AEs	Toxicity grade or conditions (CTCAEv4.0)	Action taken to pembrolizumab	irAE management with corticosteroid and/or other therapies	Monitor and follow-up
Pneumonitis	Grade 2	Withhold	
 • Administer corticosteroids (initial dose of 1-2 mg/kg prednisone or equivalent) followed by taper 	
 • Monitor participants for signs and symptoms of pneumonitis • Evaluate participants with suspected pneumonitis with radiographic imaging and initiate corticosteroid treatment • Add prophylactic antibiotics for opportunistic infections
	Grade 3 or 4, or recurrent Grade 2	Permanently discontinue		
Diarrhea / Colitis	Grade 2 or 3	Withhold	
 • Administer corticosteroids (initial dose of 1-2 mg/kg prednisone or equivalent) followed by taper 	
 • Monitor participants for signs and symptoms of enterocolitis (ie, diarrhea, abdominal pain, blood or mucus in stool with or without fever) and of bowel perforation (ie, peritoneal signs and ileus). • Participants with \geq Grade 2 diarrhea suspecting colitis should consider GI consultation and performing endoscopy to rule out colitis. • Participants with diarrhea/colitis should be advised to drink liberal quantities of clear fluids. If sufficient oral fluid intake is not feasible, fluid and electrolytes should be substituted via IV infusion.
	Grade 4	Permanently discontinue		
AST / ALT elevation or Increased bilirubin	Grade 2	Withhold	
 • Administer corticosteroids (initial dose of 0.5- 1 mg/kg prednisone or equivalent) followed by taper 	
 • Monitor with liver function tests (consider weekly or more frequently until liver enzyme value returned to baseline or is stable)
	Grade 3 or 4	Permanently discontinue		
Type 1 diabetes mellitus (T1DM) or Hyperglycemia	Newly onset T1DM or Grade 3 or 4 hyperglycemia associated with evidence of β -cell failure	Withhold	
 • Initiate insulin replacement therapy for participants with T1DM • Administer anti-hyperglycemic in participants with hyperglycemia 	
 • Monitor participants for hyperglycemia or other signs and symptoms of diabetes.
Hypophysitis	Grade 2	Withhold	
 • Administer corticosteroids and initiate hormonal replacements as clinically indicated. 	
 • Monitor for signs and symptoms of hypophysitis (including hypopituitarism and adrenal insufficiency)
	Grade 3 or 4	Withhold or permanently discontinue ¹		

Hyperthyroidism	Grade 2	Continue	
 Treat with non-selective beta-blockers (eg, propranolol) or thionamides as appropriate 	
 Monitor for signs and symptoms of thyroid disorders.
	Grade 3 or 4	Withhold or permanently discontinue ¹		
Hypothyroidism	Grade 2-4	Continue	
 Initiate thyroid replacement hormones (eg, levothyroxine or liothyroinine) per standard of care 	
 Monitor for signs and symptoms of thyroid disorders.
Nephritis and Renal dysfunction	Grade 2	Withhold	
 Administer corticosteroids (prednisone 1-2 mg/kg or equivalent) followed by taper. 	
 Monitor changes of renal function
	Grade 3 or 4	Permanently discontinue		
Myocarditis	Grade 1 or 2	Withhold	
 Based on severity of AE administer corticosteroids 	
 Ensure adequate evaluation to confirm etiology and/or exclude other causes
	Grade 3 or 4	Permanently discontinue		
All other immune-related AEs	Intolerable/ persistent Grade 2	Withhold	
 Based on type and severity of AE administer corticosteroids 	
 Ensure adequate evaluation to confirm etiology and/or exclude other causes
	Grade 3	Withhold or discontinue based on the type of event. Events that require discontinuation include and not limited to: Gullain-Barre Syndrome, encephalitis		
	Grade 4 or recurrent Grade 3	Permanently discontinue		

1. Withhold or permanently discontinue pembrolizumab is at the discretion of the investigator or treating physician.

NOTE:
For participants with Grade 3 or 4 immune-related endocrinopathy where withhold of pembrolizumab is required, pembrolizumab may be resumed when AE resolves to ≤ Grade 2 and is controlled with hormonal replacement therapy or achieved metabolic control (in case of T1DM).

Dosing interruptions are permitted in the case of medical/surgical events or logistical reasons not related to study therapy (e.g., elective surgery, unrelated medical events, patient vacation, and/or holidays). Patients should be placed back on study therapy within 3 weeks of the scheduled interruption, unless otherwise discussed with the Sponsor. The reason for interruption should be documented in the patient's study record.

If treatment is delayed by more than 20 days from the planned date of dose administration, patient will be considered to have missed the dose for that cycle and will proceed to the next cycle. Missed cycle doses will not be made up.

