4.12 Efficacy of Pembrolizumab in Lung Cancer

The safety and efficacy of PD 1 inhibition with pembrolizumab in patients with advanced non-small cell has been investigated in a phase I clinical trial (48). Four hundred and ninety five patients with advanced NSCLC were treated with pembrolizumab (at a dose of either 2mg or 10mg per kilogram every 2 weeks or 10 mg per kilogram every 2 weeks). Treatment-related adverse events occurred in 351 patients (70.9%), with no clear difference according to dose or schedule. The most common treatment-related adverse events were fatigue, pruritus, and decreased appetite. Adverse events of grade 3 or higher were reported in 47 of 495 patients (9.5%). The only treatment-related adverse events of an inflammatory or immune-mediated nature that occurred in more than 2% of patients were infusion-related reactions (in 15 patients [3.0%]), hypothyroidism (in 34 patients [6.9%]), and pneumonitis (in 18 patients [3.6%]). One infusion reaction led to treatment discontinuation. All the patients with hypothyroidism were successfully treated with medical therapy. Pneumonitis of grade 3 or greater was observed in 9 patients (1.8%), including 1 (0.2%) who died. The overall response rate was 19.4% (95% confidence interval [CI], 16.0 to 23.2), which included a response rate of 18.0% (95% CI, 14.4 to 22.2) in the 394 previously treated patients and 24.8% (95% CI, 16.7 to 34.3) in the 101 previously untreated patients. The best overall response was stable disease in 21.8% of patients. The response rate was similar regardless of dose, schedule, and histologic analysis.

At the time of this analysis, 84.4% of patients with a response had no disease progression, and the median duration of response was 12.5 months (range, 1.0 to 23.3) in all patients, 10.4 months (range, 1.0 to 10.4) in previously treated patients, and 23.3 months (range, 1.0 to 23.3) in previously untreated patients. Median progression-free survival was 3.7 months (95% CI, 2.9 to 4.1) for all the patients, 3.0 months (95% CI, 2.2 to 4.0) for previously treated patients, and 6.0 months (95% CI, 4.1 to 8.6) for previously untreated patients. Median overall survival was 12.0 months (95% CI, 9.3 to 14.7) for all the patients, 9.3 months (95% CI, 8.4 to 12.4) for previously treated patients, and 16.2 months (95% CI, 16.2 to not reached) for previously untreated patients.

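### Table 7 withholds pembrolizumab for Grade 1 myocarditis, but its general restart rule permits re-dosing while myocarditis persists at Grade 1

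*Combined protocol and SAP*

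**What the plan says.** Section 10.1 makes the table binding: "Pembrolizumab must be withheld for drug-related toxicities and severe or life-threatening AEs as per Table 7 below". The myocarditis row of Table 7 withholds at Grade 1 or 2 and discontinues permanently at Grade 3 or 4.

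Three general instructions stand above the rows. Instruction 1 governs steroids: "Corticosteroid taper should be initiated upon AE improving to Grade 1 or less and continue to taper over at least 4 weeks". Instruction 2 governs restart. It opens "For situations where pembrolizumab has been withheld" and continues that "pembrolizumab can be resumed after AE has been reduced to Grade 1 or 0 and corticosteroid has been tapered". It then sets an outer limit: "Pembrolizumab should be permanently discontinued if AE does not resolve within 12 weeks of last dose". Failure to bring the steroid down to 10 mg prednisone or equivalent per day within 12 weeks also ends treatment.

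The only event-specific restart rule is the NOTE under the table. It opens "For participants with Grade 3 or 4 immune-related endocrinopathy where withhold of pembrolizumab is required" and says that "pembrolizumab may be resumed when AE resolves to ≤ Grade 2 and is controlled with hormonal replacement therapy", or when metabolic control is achieved in type 1 diabetes. Footnote 1, on investigator discretion, is attached only to the Grade 3 or 4 cells for hypophysitis and hyperthyroidism. Table 4 in Section 8.8, on supportive care, has no myocarditis entry.

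**The concern.** A restart rule normally asks for a better state than the one that triggered the hold. For myocarditis the general rule does not: Grade 1 is both a grade that stops dosing and a grade at which dosing may begin again. A site that follows the instructions as written can therefore give pembrolizumab to a patient with ongoing Grade 1 myocarditis, the one toxicity for which the table withholds at so low a grade.

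What is at stake is the safety of an individual patient, and consistency between the two sites if one re-dosed at Grade 1 and the other waited for Grade 0. The trial's statistical conclusions are not at stake.

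**Working it through.** No figure in the plan is to be reproduced here. The check sets each row's withhold grades against the restart grades in general instruction 2 (Grade 1 or 0).

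| Table 7 row | Lowest grade that withholds | General restart ceiling | Overlap? |
|---|---|---|---|
| Pneumonitis | 2 | 1 | No |
| Diarrhoea/colitis | 2 | 1 | No |
| AST/ALT or bilirubin | 2 | 1 | No |
| Type 1 diabetes or hyperglycaemia | New-onset diabetes, or 3 | 1 | No |
| Hypophysitis | 2 | 1 | No under instruction 2; see the NOTE below |
| Hyperthyroidism | 3 (withhold or discontinue) | 1 | No |
| Hypothyroidism | None (continue) | – | No |
| Nephritis and renal dysfunction | 2 | 1 | No |
| **Myocarditis** | **1** | **1** | **Yes** |
| All other immune-related events | 2 (intolerable or persistent) | 1 | No |

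**Grade 2 onset.** Dosing is withheld. The event improves to Grade 1, and the steroid, if used, is tapered over at least 4 weeks. Both conditions of instruction 2 are now met and dosing may restart, although the event still has a grade that the row lists under withhold.

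**Grade 1 onset.** Dosing is withheld at a grade that already meets the grade part of the restart rule. Only the steroid condition remains, and it has no force if no steroid was given. One could insist that an event must be *reduced* to meet the rule, so that a Grade 1 event has to reach Grade 0. The milder onset would then face the stricter restart rule, which is hard to take as intended.

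**The NOTE.** Hypophysitis withholds at Grade 2, and the NOTE lets Grade 3 or 4 hypophysitis restart at Grade 2. Here too a restart grade equals a withhold grade. But the NOTE says so expressly, limits it to Grade 3 or 4 endocrinopathy, and requires hormonal or metabolic control. Myocarditis has no comparable line.

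**The 12-week limit.** It attaches no grade to resolution, and restart can come before week 12. It does not close the gap.

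**Frequency.** The documents give no myocarditis rate. Section 4.12 introduces a list as "The only treatment-related adverse events of an inflammatory or immune-mediated nature that occurred in more than 2% of patients" among 495 patients, and myocarditis is not on it. Since 0.02 × 495 = 9.9, at most 9 of 495 (1.8%) had it. That is a ceiling set by a reporting threshold, not an estimate, and it comes from pembrolizumab without SABR. The affected patients are a subset of those with myocarditis. The figure shows only that the case is rare.

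**The case against.** The strongest reply is that the two texts cover different steps. The row says what to do when the event occurs; instruction 2 says when dosing may resume. No row contains a restart rule, so only one text answers the restart question. The wording is also permissive, so a site that keeps withholding breaches nothing. The hypophysitis case shows that the table can let a restart provision govern at a grade that is also a withhold grade.

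Much of this stands. A reader might infer that Table 7 contradicts itself by giving two answers for the same patient. The documents do not support that: the sequential reading is natural and yields one answer. The point is that this answer is restart at Grade 1, which leaves the Grade 1 withhold with little effect. The hypophysitis precedent helps the reply only in part, because that exception is written out and carries a condition.

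There are also safeguards. The steroid must be tapered, the row calls for evaluation to confirm the cause, the investigator may withdraw a patient from treatment (Section 7.6), and serious events are reviewed in real time (Section 17.3). These limit the consequence, but none sets a restart grade for myocarditis.

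Finally, nothing in the documents says that myocarditis must reach Grade 0. That is correct, and the fix is offered as a proposal.

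**Conclusion.** The point holds as a minor patient-safety improvement. As written, and on its most natural reading, the protocol permits pembrolizumab to restart during persistent Grade 1 myocarditis, while the same table makes Grade 1 myocarditis a reason to withhold. Myocarditis is the only row where the general restart ceiling meets the withhold threshold.

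The conclusion rests on reading the row as the action at onset and instruction 2 as the restart rule. The protocol does not state that division, but it fits the layout of the table.

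Two further inferences should not be drawn. One is a maximum number of doses that could fall in the overlap before week 12: the limit runs from the last dose, so a restart dose begins a new 12-week period and no fixed cap follows. The other is a probability that one of the 32 patients is affected: it would need a myocarditis rate and the share of cases that persist at Grade 1, and the documents give neither.

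No endpoint, sample size or analysis changes.

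**What to change.** Add to the myocarditis Grade 1 or 2 row: *Resume only after resolution to Grade 0 and completion of any corticosteroid taper; otherwise permanently discontinue at 12 weeks from last dose.* Add to general instruction 2: *except myocarditis, see row.*

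Grade 0 places the restart grade below the lowest withhold grade, as instruction 2 already does for the other non-endocrine rows. If the sponsor does intend restart at Grade 1, one sentence saying so would remove the doubt, though it would keep the exposure described here.

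The change can be made by amendment or clarification letter, with no effect on visits, sample size or analysis. Its clinical cost is that a rare patient with persistent Grade 1 myocarditis would not restart pembrolizumab.
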